### **3.2.4 Monitoring of Everolimus suspected toxicities**

Patients whose treatment is interrupted or permanently discontinued due to an adverse event or abnormal laboratory value suspected to be related to Everolimus must be followed at least weekly until the adverse event or abnormal laboratory resolves or returns to grade 1. If a patient requires a dose delay of > 21 days from the intended day of the next scheduled dose, then the patient must be discontinued from the study.

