Grade 4 Neutropenia (neutrophils <math><0.5 \times 10^9/L</math>)	Interrupt Everolimus until recovery to grade $\leq 1$ (neutrophils $\geq 1.5 \times 10^9/L$ ). Then resume Everolimus at the lower dose level. If grade 3 or grade 4 neutropenia occurs despite this dose reduction, discontinue Everolimus.
Grade 3 febrile neutropenia (not life-threatening)	Interrupt Everolimus until resolution of fever and neutropenia to grade $\leq 1$ . Hold further Everolimus until the ANC $\geq 1,500/\text{mm}^3$ and fever has resolved. Then resume Everolimus at the lower dose level. If febrile neutropenia recurs, discontinue Everolimus.
Grade 4 febrile neutropenia (life-threatening)	Discontinue Everolimus.
Any hematological or non-hematological toxicity requiring interruption for $\geq 3$ weeks	Discontinue Everolimus.

\*Grade 3 hyperlipidemia (hypercholesterolemia and/or hypertriglyceridemia) should be managed using medical therapies (see Sec. 3.2.5.2).

Subjects who require anticoagulation after randomization should be treated according to their physician's discretion and can continue on study. Since everolimus can interact with warfarin, the use of low-molecular weight heparins or non-coumarin containing anticoagulants is encouraged. If warfain is administered, close monitoring of INR is warranted.

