### **3.2.5.3 Management of non-infectious pneumonitis**

Non-infectious pneumonitis is a class effect of rapamycin derivatives. Cases of non-infectious pneumonitis (including interstitial lung disease) have also been described in patients taking everolimus (see [Section 5](#) Adverse drug reactions). Some of these have been severe and on rare occasions, a fatal outcome was observed.

A diagnosis of non-infectious pneumonitis should be considered in patients presenting with non-specific respiratory signs and symptoms such as hypoxia, pleural effusion, cough or dyspnoea, and in whom infectious, neoplastic and other non-medicinal causes have been excluded by means of appropriate investigations. Patients should be advised to report promptly any new or worsening respiratory symptoms.

Patients who develop radiological changes suggestive of non-infectious pneumonitis and have few or no symptoms may continue everolimus therapy without dose alteration. If symptoms are moderate (Grade 2), consideration should be given to interruption of therapy until

symptoms improve. The use of corticosteroids may be indicated. Everolimus may be reintroduced at a reduced dose until recovery to Grade 1 or better.

For cases where symptoms of non-infectious pneumonitis are severe (Grade 3), everolimus therapy should be discontinued and the use of corticosteroids may be indicated until clinical symptoms resolve. Therapy with everolimus may be re-initiated at a reduced dose depending on the individual clinical circumstances.

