**Table 3-5 Management of non-infectious pneumonitis**

Worst Grade Pneumonitis	Required Investigations	Management of Pneumonitis	Everolimus Dose Adjustment
Grade 1	CT scans with lung windows and pulmonary function testing including: spirometry, DLCO, and room air O2 saturation at rest. Repeat chest x-ray/CT scan every 2 Cycles until return to baseline.	No specific therapy is required	Administer 100% of Everolimus dose.
Grade 2	CT scan with lung windows and pulmonary function testing including: spirometry, DLCO, and room air O2 saturation at rest. Repeat each subsequent Cycle until return to baseline. Consider bronchoscopy *	Symptomatic only. Prescribe corticosteroids if cough is troublesome.	Reduce Everolimus dose until recovery to ≤ Grade 1. Everolimus may also be interrupted if symptoms are troublesome. Patients will be withdrawn from the study if they fail to recover to ≤ Grade 1 within 3 weeks.
Grade 3	CT scan with lung windows and pulmonary function testing including: spirometry, DLCO, and room air O2 saturation at rest; Repeat each subsequent Cycle until return to baseline. Bronchoscopy is recommended *	Prescribe corticosteroids if infective origin is ruled out. Taper as medically indicated.	Hold treatment until recovery to ≤ Grade 1. May restart protocol treatment within 3 weeks at a reduced dose (by one level) if evidence of clinical benefit. Patients will be withdrawn from the study if they fail to recover to ≤ Grade 1 within 3 weeks.
Grade 4	CT scan with lung windows and required pulmonary function testing includes: spirometry, DLCO, and room air O2 saturation at rest. Repeat each subsequent Cycle until return to baseline. Bronchoscopy is recommended *	Prescribe corticosteroids if infective origin is ruled out. Taper as medically indicated.	Discontinue treatment.

\*A bronchoscopy with biopsy and/or bronchoalveolar lavage is recommended.

All interruptions or changes to study drug administration must be recorded.

It will be documented whether or not each patient completed the clinical study. If for any patient either study treatment or observations were discontinued the reason will be recorded. Reasons that a patient may discontinue participation in a clinical study are considered to constitute one of the following:

1. adverse event(s)
2. abnormal laboratory value(s)

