### **3.3 Treatments**

#### **3.3.1 Everolimus Administration**

The study drug Everolimus or placebo will be self-administered (by the patients themselves). The investigator will instruct the patient to take the study drug exactly as specified in the protocol. Everolimus /placebo will be administered orally as once daily dose of 10 mg (two 5 mg tablets) continuously from study day 1 until progression of disease, unacceptable toxicity, or 1 year from start of therapy. Patients will be instructed to take Everolimus /placebo in the morning, at the same time each day. Everolimus /placebo can be taken with or without food (a low-fat meal is recommended). Dietary habits around the time of Everolimus /placebo intake should be as consistent as possible throughout the study. If vomiting occurs, no attempt should be made to replace the vomited dose. All dosages prescribed and dispensed to the patient and all dose changes during the study must be recorded.

Medication labels will comply with US legal requirements and be printed in English. They will supply no information about the patient. The storage conditions for study drug will be described on the medication label.

For this trial, Everolimus and placebo are supplied, by Novartis, 10 tablets per card. Tablets should be opened only at the time of administration as drug is both hygroscopic and light-sensitive. Drug request forms will be provided to use when ordering Everolimus and placebo. Everolimus will only be shipped once all required regulatory documents are received.

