### 3.3.3 Concomitant therapy

Patients will be instructed not to take any additional medications (including over-the-counter products) during the course of the study without prior consultation with the investigator. At each visit, the investigator will ask the patient about any new medications he/she is or has taken after the start of the study drug.

All Concomitant medications/Significant non-drug therapies taken  $\leq$  30 days prior to start and after start of study drug, including physical therapy and blood transfusions, should be recorded.

The following restrictions apply during the entire duration of the study:

- No other investigational therapy should be given to patients.
- No anticancer agents other than the study medication should be given to patients. If such agents are required for a patient then the patient must first be withdrawn from the study.
- Oral contraceptives in preclinical and clinical data have shown everolimus to have CYP3A4 inhibitory activity rather than induction activity, induction of metabolism of contraceptive hormones by everolimus is unlikely. Consequently, administration of everolimus should not reduce the efficacy of oral contraceptives.
- Growth factors (e.g. G-CSF, GM-CSF, erythropoietin, platelets growth factors etc.) are not to be administered prophylactically but may be prescribed by the investigator for rescue from severe hematologic events, if this is thought to be appropriate.
- Concurrent administration of Everolimus and strong CYP3A4 inhibitors (such as ketoconazole, itraconazole, ritonavir) and inducers (such as rifampin, rifabutin) should be avoided. Provided there is no alternative treatment available, patients should be closely monitored for potential toxicities.
- Concurrent administration of Everolimus and moderate CYP3A4 inhibitors (such as erythromycin, fluconazole, calcium channel blockers, benzodiazepines) and moderate CYP3A4 inducers (e.g. carbamazepine, phenobarbital, phenytoin) should also be avoided if possible, or used subject to caution (e.g. increased frequency of safety monitoring, temporary interruption of Everolimus).
- Competitive inhibition could occur when Everolimus is combined with drugs which are also CYP3A4 substrates. Therefore caution should be exercised in such cases.

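### Study-exit wording in 3.2.4 and Table 3-5 conflicts with 2-year imaging for all patients, and neither progression follow-up after exit nor PFS censoring is stated

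*Combined protocol and SAP*

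**What the plan says.** **Long interruptions.** The last row of Table 3-1 (section 3.2.3) covers "Any hematological or non-hematological toxicity requiring interruption for" 3 weeks or more. Its action is to stop everolimus; leaving the study is not mentioned. Section 3.2.4 takes a delay of more than 21 days "from the intended day of the next scheduled dose, then the patient must be discontinued from the study".

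**Pneumonitis.** For grades 2 and 3, the dose-adjustment column of Table 3-5 says: "Patients will be withdrawn from the study if they fail to recover to ≤ Grade 1 within 3 weeks". The text of 3.2.5.3 on grade 3 says only that "everolimus therapy should be discontinued and the use of corticosteroids may be indicated until clinical symptoms resolve". Table 3-5 treats grade 4 as a treatment stop.

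**Follow-up.** Section 3.1 sets a 2-year minimum of radiographic follow-up for all patients. Footnote 3 of Table 3-4 schedules imaging every 4-6 months in years 1 and 2 with no condition on treatment status. Section 3.2.4 keeps some contact after a toxicity stop: such patients "must be followed at least weekly until the adverse event or abnormal laboratory resolves or returns to grade 1". The text after Table 3-5 says: "If for any patient either study treatment or observations were discontinued the reason will be recorded". Section 4.6 ends the recording of new adverse events for patients who discontinue the study and keeps everyone in survival follow-up.

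**Analysis.** Section 6.1 names 2-year PFS as the primary endpoint, estimated by Kaplan-Meier and compared by a stratified logrank test. Neither 6.1 nor 3.4.3 states a censoring rule, an analysis population or the handling of patients who leave.

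**The concern.** PFS needs scheduled disease assessment until progression or death. A patient taken off the study for toxicity may, on a literal reading, have no further scans. Deaths would still be known through the survival follow-up in 4.6, but 6.1 does not say whether a death after exit counts as a PFS event or whether the patient is censored at exit.

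The group at issue is selected by toxicity, and toxicity differs by arm in the protocol's own data. Section 3.2.5 reports permanent stops for adverse reactions of 7% on everolimus and 0% on placebo in the renal cancer trial, and grade 3 or 4 reactions of 39% and 7%. Unequal exits are therefore plausible. If exit is also related to the risk of relapse, censoring at exit biases the comparison of arms. In a multicentre trial, sites could also follow different sentences of the same protocol.

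**Working it through.** **1. The passages side by side.**

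| Place | Trigger | Stated consequence |
|---|---|---|
| Table 3-1, last row | toxicity interruption of 3 weeks or more | stop everolimus |
| 3.2.4 | dose delay over 21 days | discontinued from the study |
| Table 3-5, grades 2-3 | no recovery to grade 1 or better within 3 weeks | withdrawn from the study |
| 3.1 | none; all patients | at least 2 years of imaging |

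The first two rows differ in consequence and at the boundary: an interruption of exactly 21 days meets only Table 3-1. The study exits in rows 2 and 3, taken literally, cannot be squared with row 4. The wording is hard to dismiss as loose, because for a third grade 3 neutropenia Table 3-1 specifies removal from study therapy, so the protocol has a term for a treatment-only stop.

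**2. The plan's own figure.** Monthly hazards are -ln(0.50)/24 = 0.02888 and -ln(0.70)/24 = 0.01486, a ratio of 1.94, with medians of 24.0 and 46.6 months, as stated in 6.1. With 36 months' accrual and 24 months' follow-up, event probabilities are 0.689 and 0.458. The expected number of events is 66 × (0.689 + 0.458) = 75.7, and power at N = 132 is 80.3% (difference-of-hazards formula). The design reproduces; the point concerns conduct and analysis rules.

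**3. Possible bias in 2-year PFS.** Assumptions: a share w = 7% of each arm has hazard r × h and the rest have h; only those on everolimus exit, and they are censored at exit; true 2-year PFS is 50% in both arms. The 7% is borrowed from 3.2.5. The values of r are assumed; no document gives one.

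Solve (1 - w)·exp(-24h) + w·exp(-24rh) = 0.50 for h. With exit at month 6, the Kaplan-Meier limit is [(1 - w)·exp(-6h) + w·exp(-6rh)] × exp(-18h).

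For r = 2: h = 0.02745. The bracket is 0.93 × 0.8481 + 0.07 × 0.7194 = 0.8391; the second factor is 0.6101; the product is 0.512.

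Spreading exits uniformly over months 0-12 changes the results by less than 0.1 points. On that basis, with null logrank simulations (80 per arm, 20,000 trials; unstratified, so a simplification of the planned test):

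| r | h | Estimated 2-year PFS | Rejection favouring everolimus (nominal 2.5%) | Two-sided rejection (nominal 5%) |
|---|---|---|---|---|
| 0.5 | 0.03013 | 48.9% | 1.6% | 5.7% (1.6 + 4.1) |
| 1 | 0.02888 | 50.0% | 2.5% | about 5% |
| 2 | 0.02745 | 51.2% | 3.5% | 5.3% |
| 3 | 0.02672 | 51.7% | 4.0% | 5.6% |

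**4. More exits.** With w = 20% and exit at month 6, the same formula gives 46.6% at r = 0.5 (h = 0.03271; 0.8388 × 0.5551), 53.4% at r = 2 and 54.9% at r = 3. Two-sided error is 6.9% at r = 2 and 8.9% at r = 3 (8,000 trials).

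**5. Precision.** Simulated power with all 160 patients followed is 88.7%. If exits are unrelated to prognosis and censored, it is 87.5% for 7% vs 0% exits and 85.5% for 20% vs 0%. It falls to 79.6% only if the grade 3-4 reaction rates of 39% vs 7% are taken as exit rates.

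**The case against.** The best defence is that the protocol means a treatment stop throughout. Section 3.1 promises imaging to all; Table 3-4 attaches no treatment condition; 3.2.4 itself keeps weekly contact after a permanent stop; the Table 3-5 wording sits in a dose-adjustment column; and the text after that table distinguishes treatment from observation. Section 3.3.1 has dosing run "continuously from study day 1 until progression of disease, unacceptable toxicity, or 1 year from start of therapy", which makes toxicity an end of dosing and says nothing of leaving the study. The silence of 4.6 on progression is weak evidence, since that section is about adverse-event reporting. A site can also obey Table 3-1 and 3.2.4 together, because leaving the study includes stopping the drug; the real incompatibility is with 3.1. All of this stands. It makes continued follow-up the likelier intention, but does not put it in the text.

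A reader might infer more than the documents bear:

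- *That the gap favours everolimus.* This needs leavers to have a higher hazard than the others. With a lower hazard the sign reverses, and nothing in the documents fixes either.
- *That 7% is the expected exit rate.* It counts drug stops in another disease, at a median exposure of 141 days against up to a year here. Several Table 3-1 stops, such as grade 4 toxicity, involve no study exit. The true share could be lower or higher.
- *That 3.3.3 contradicts Table 3-1.* On other anticancer agents it says "If such agents are required for a patient then the patient must first be withdrawn from the study". That is a different trigger and bears mainly on second primaries treated before progression.
- *That safety data are broadly lost.* Serious events to 30 days (3.4.4.2) and suspected-related events throughout follow-up (4.6) remain reportable.

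**Conclusion.** The inconsistency is real and should be fixed. The documents use study exit in two places and promise imaging to all in another. They do not say whether progression is assessed after exit, or how leavers enter the primary analysis. They do not establish that sites will stop scanning these patients.

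If sites did so, the likely numerical effect is small at the only rate the documents offer: between -1.1 and +1.7 percentage points on a 2-year PFS of 50%, with two-sided error of about 5 to 6%. That range rests on assumed exits (7%, everolimus only), censoring at exit, and leavers' hazards of 0.5 to 3 times the others'. Direction and size are both unknown, and the bias grows with the number of unequal exits. The 20% loss allowance in 6.1 protects precision. It does not protect against bias, and the plan does not say whether protocol-mandated exits count towards it.

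**What to change.** 1. Reconcile 3.1, Table 3-1, 3.2.4 and Table 3-5 (with the text of 3.2.5.3) so that stopping study treatment is distinct from leaving the study. This takes no position on the clinical stopping rules or the interruption limit, which the sponsor must reconcile.
2. Add to 3.4.2 or 3.4.3: *After treatment stops for any reason, imaging and progression follow-up continue on the existing schedule until progression, death, withdrawal of consent, loss to follow-up or end of study.*
3. Add to 6.1: *All randomised patients are analysed by assigned arm. PFS is not censored when treatment stops. Patients without progression or death are censored at the last disease assessment. Study exits are reported by arm with timing and reason.*
4. State in 6.1 how other anticancer therapy and second primaries are handled in PFS. That choice is the sponsor's.

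Items 2 and 3 are both needed: a censoring rule cannot recover progression that was never assessed, and continued scans do not by themselves define the analysis.

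The cost is protocol wording plus scans that 3.1 and Table 3-4 already schedule. At the 7% proxy this concerns at most 0.07 × 80 = 5.6 everolimus patients, of whom about 4 to 5 would leave before an event.

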### **3.2.5 Known Undesirable Side Effects of Everolimus**

The data described below reflect exposure to everolimus (n=274) and placebo (n=137) in a randomized phase III study for the treatment of metastatic renal cell carcinoma. In total, 165 patients were exposed to everolimus 10 mg/day for  $\geq$ 4 months. The median age of patients was 61 years (range 27 to 85). The most common adverse reactions (incidence  $\geq$ 10%) were stomatitis, rash, fatigue, asthenia, diarrhea, anorexia, nausea, mucosal inflammation, vomiting, cough, peripheral edema, infections, dry skin, epistaxis, pruritus, and dyspnoea. The most common grade 3-4 adverse reactions (incidence  $\geq$ 2%) were infections, stomatitis, fatigue, and pneumonitis.

The median duration of blinded study treatment was 141 days (range 19 to 451) for patients receiving everolimus and 60 days (range 21 to 295) for those receiving placebo. The rates of treatment-emergent adverse reactions resulting in permanent discontinuation were 7% and 0% for the everolimus and placebo treatment groups, respectively. Most treatment-emergent adverse reactions were grade 1 or 2 in severity. Grade 3 or 4 treatment-emergent adverse reactions were reported in 39% versus 7% of patients receiving everolimus and placebo, respectively. Deaths due to acute respiratory failure (0.7%), infection (0.7%), and acute renal failure (0.4%) were observed on the everolimus arm.

Everolimus has immunosuppressive properties and may predispose patients to bacterial, fungal, viral or protozoan infections, including infections with opportunistic pathogens. Localized and systemic infections, including pneumonia, other bacterial infections, invasive fungal infections, such as aspergillosis or candidiasis and viral infections including reactivation of hepatitis B virus, have been described in patients taking everolimus. Some of these infections have been severe (e.g. leading to respiratory or hepatic failure) and occasionally have had a fatal outcome.

Physicians and patients should be aware of the increased risk of infection with everolimus. Treat pre-existing infections prior to starting treatment with everolimus. While taking everolimus, be vigilant for symptoms and signs of infection; if a diagnosis of infection is made, institute appropriate treatment promptly and consider interruption or discontinuation of everolimus. If a diagnosis of invasive systemic fungal infection is made, discontinue everolimus and treat with appropriate antifungal therapy.

Reactivation of Hepatitis B (HBV) has been observed in patients with cancer receiving chemotherapy (Yeo 2004). Sporadic cases of Hepatitis B reactivation have also been seen in this setting with everolimus. Use of antivirals during anti-cancer therapy has been shown to reduce the risk of Hepatitis B virus reactivation and associated morbidity and mortality (Loomba 2008). A detailed assessment of Hepatitis B/C medical history and risk factors must

be done for all patients at screening, with testing performed prior to the first dose of everolimus.

Hypersensitivity reactions manifested by symptoms including, but not limited to, anaphylaxis, dyspnea, flushing, chest pain or angioedema (e.g. swelling of the airways or tongue, with or without respiratory impairment) have been observed with everolimus.

Hyperglycemia has been reported in clinical trials. Monitoring of fasting serum glucose is recommended prior to the start of everolimus therapy and periodically thereafter. Optimal glycemic control should be achieved before starting a patient on everolimus. Mouth ulcers, stomatitis and oral mucositis have been seen in patients treated with everolimus. In such cases topical treatments are recommended, but alcohol- or peroxide-containing

Elevations of serum creatinine, usually mild, have been reported in clinical trials. Monitoring of renal function, including measurement of blood urea nitrogen (BUN) or serum creatinine, is recommended prior to the start of everolimus therapy and periodically thereafter.

Decreased hemoglobin, lymphocytes, platelets and neutrophils have been reported in clinical trials. Monitoring of complete blood count is recommended prior to the start of everolimus therapy and periodically thereafter.

Everolimus is not recommended in patients with severe hepatic impairment, (Child-Pugh class C).

The use of live vaccines and close contact with those who have received live vaccines should be avoided during treatment with everolimus. **Close contact with those who have received attenuated live vaccines should be avoided during treatment with everolimus. Examples of live vaccines include intranasal influenza, measles, mumps, rubella, oral polio, BCG, yellow fever, varicella and TY21a typhoid vaccines.**

Hypophosphatemia, hypomagnesemia, hyponatremia and hypocalcemia have been reported as serious adverse reactions. Electrolytes should be monitored in patients treated with Everolimus.

**Table 3-1** provides general recommendations for the management of patients, with suspected drug toxicities while on treatment with Everolimus as single-agent therapy.

More detailed information regarding Everolimus reported suspected toxicities and individual cases is provided in the [Investigator's Brochure](#).

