### 3.2.3 Interruption or discontinuation of treatment

For patients who are unable to tolerate the protocol-specified dosing schedule, dose adjustments are permitted in order to keep the patient on study drug. If administration of Everolimus must be interrupted because of unacceptable toxicity, drug dosing will be interrupted or modified according to rules described in [Table 3-1](#). Toxicity will be assessed using the NIH-NCI Common Terminology Criteria for Adverse Events, version 4.0 (CTCAEv4.0, ([http://evs.nci.nih.gov/ftp1/CTCAE/CTCAE\\_4.03\\_2010-06-14\\_QuickReference\\_5x7.pdf](http://evs.nci.nih.gov/ftp1/CTCAE/CTCAE_4.03_2010-06-14_QuickReference_5x7.pdf))).

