**Table 3.0 Everolimus dose level modification guidelines**

Dose level	Dose and schedule
0 (starting dose)	10 mg daily
-1	5 mg daily
-2	5 mg every other day

**Table 3-1 Criteria for dose-modification in case of suspected Everolimus  
Everolimus toxicity and re-initiation of Everolimus treatment**

Toxicity	Actions
Non-hematological toxicity	
Grade 2 (except pneumonitis – refer to Table 3-2)	If the toxicity is tolerable to the patient, maintain the same dose. If the toxicity is intolerable to patient, interrupt Everolimus until recovery to grade $\leq 1$ . Then reintroduce Everolimus at same dose. If event returns to grade 2, then interrupt Everolimus until recovery to grade $\leq 1$ . Then reintroduce Everolimus at the lower dose level.
Grade 3 (except hyperlipidemia*) (except pneumonitis – refer to Table 3-2)	Interrupt Everolimus until recovery to grade $\leq 1$ . Then reintroduce Everolimus at the lower dose level. For pneumonitis consider the use of a short course of corticosteroids.
Grade 4	Discontinue Everolimus.
Hematological toxicity	
Grade 2 Thrombocytopenia (platelets <math><75, \geq 50 \times 10^9/L</math>)	Interrupt Everolimus until recovery to grade $\leq 1$ ( $>75 \times 10^9/L$ ). Then reintroduce Everolimus at initial dose. If thrombocytopenia again returns to grade 2, interrupt Everolimus until recovery to grade $\leq 1$ . Then reintroduce Everolimus at the lower dose level.
Grade 3 Thrombocytopenia (platelets <math><50, \geq 25 \times 10^9/L</math>)	Interrupt Everolimus until recovery to grade $\leq 1$ (platelets $\geq 75 \times 10^9/L$ ). Then resume Everolimus at one dose level lower. If grade 3 thrombocytopenia recurs, discontinue Everolimus.
Grade 4 Thrombocytopenia (platelets <math><25 \times 10^9/L</math>)	Discontinue Everolimus.
Grade 3 Neutropenia (neutrophils <math><1, \geq 0.5 \times 10^9/L</math>)	Interrupt Everolimus until recovery to grade $\leq 1$ (neutrophils $\geq 1.5 \times 10^9/L$ ). Then resume Everolimus at the initial dose. If ANC again returns to Grade 3, hold Everolimus until the ANC $\geq 1.5 \times 10^9/L$ . Then resume Everolimus dosing at the lower dose level. Discontinue patient from study therapy for a third episode of grade 3 neutropenia.

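### Section 3.2.5 says to discontinue everolimus for invasive systemic fungal infection, but Table 3-1 makes no exception for it and lets a grade 3 event restart

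*Combined protocol and SAP*

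**What the plan says.** Section 3.2.5 deals with infections in two steps. For infection in general, it asks the physician only to consider interrupting or stopping everolimus. For one named diagnosis it is firmer: "If a diagnosis of invasive systemic fungal infection is made, discontinue everolimus and treat with appropriate antifungal therapy".

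Section 3.2.3 covers dosing once everolimus must be interrupted for unacceptable toxicity. In that case "drug dosing will be interrupted or modified according to rules described in" Table 3-1. The relevant non-hematological rows of that table are:

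- **Grade 2** (pneumonitis excepted): "If the toxicity is tolerable to the patient, maintain the same dose". If it is intolerable, hold to grade 1 or lower: "Then reintroduce Everolimus at same dose". The lower level is used only on recurrence.
- **Grade 3** (hyperlipidemia and pneumonitis excepted): hold to grade 1 or lower. "Then reintroduce Everolimus at the lower dose level. For pneumonitis consider the use of a short course of corticosteroids".
- **Grade 4:** discontinue.

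Two provisions cap the length of a hold. The last row of Table 3-1 discontinues the drug for "Any hematological or non-hematological toxicity requiring interruption for" 3 weeks or more. Section 3.2.4 adds its own limit, which applies to anyone who, in its words, "requires a dose delay of > 21 days from the intended day of the next scheduled dose, then the patient must be discontinued". The removal there is from study participation.

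Later in section 3.2.5, Table 3-1 is described as giving general recommendations for suspected drug toxicities.

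**The concern.** The table already has a way to say that a more specific rule takes over. Pneumonitis is excepted at grades 2 and 3. Hyperlipidemia is excepted at grade 3, with a footnote sending the reader to section 3.2.5.2. Invasive systemic fungal infection also has its own rule in section 3.2.5, but it has neither an exception nor a footnote. A site working from the table could reasonably take the listed exceptions as complete.

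A site also has reason to treat this infection as suspected drug toxicity and so to turn to the table. Section 3.2.5 says everolimus may predispose to fungal infection, reports invasive fungal infections in patients taking it, and says that some infections on the drug were severe and occasionally fatal. At stake is an immunosuppressive drug restarted by the table's default after an event for which the safety text says to discontinue it.

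**Working it through.** No calculation underlies the point, and the plan states no figure to reproduce. The check sets the two instructions side by side.

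**Inputs.** The fungal infection sentence in section 3.2.5; the dose levels in Table 3.0 (10 mg daily, then 5 mg daily, then 5 mg every other day); the grade rows and last row of Table 3-1; the delay limit in section 3.2.4.

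**Comparison for a patient on 10 mg daily**

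| Grade | Section 3.2.5 | Table 3-1 | Result |
|---|---|---|---|
| 2, tolerable | discontinue | stay on 10 mg | conflict, if grade 2 can occur |
| 2, intolerable | discontinue | hold, restart at 10 mg | conflict if the hold is under 3 weeks and grade 2 can occur |
| 3 | discontinue | hold, restart at 5 mg | conflict if the hold is under 3 weeks |
| 4 | discontinue | discontinue | agree |

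**Length of hold.** 3 weeks × 7 = 21 days. Table 3-1 discontinues at an interruption of 21 days or more, and section 3.2.4 acts on a delay of more than 21 days. The two hold-and-restart routes therefore depart from section 3.2.5 only when the patient recovers to grade 1 or lower in under 21 days.

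**What discontinuing means here.** Section 3.2.5 names interruption and discontinuation as separate options in its general infection sentence, then uses only the second for invasive fungal infection. So the instruction asks for more than a hold. It does not follow that the stop must be final. Section 3.2.5.3 says therapy should be discontinued for grade 3 pneumonitis and then allows re-initiation according to individual circumstances. Section 3.2.4 adds a word when it means a final stop: "Patients whose treatment is interrupted or permanently discontinued due to an adverse event or abnormal laboratory value suspected to be related to Everolimus". The difference is that section 3.2.5.3 states its restart route and the fungal infection sentence states none.

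**Size.** The documents give no incidence of invasive fungal infection. The nearest figure is in section 3.2.5: deaths from infection of any kind on everolimus in the cited renal cancer trial, 0.7% of 274, or 0.007 × 274 = 1.9, about 2 patients. It is not specific to fungal infection and does not size the problem in this trial.

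**The case against.** The strongest reply is that the specific rule is already written and governs. The fungal infection sentence is unconditional and names one diagnosis. The table sorts non-hematological events by grade, says nothing about infection, and is itself called general recommendations. This is a fair reading, and it keeps the severity low. It does not close the gap, because section 3.2.3 calls the same table rules and no text says which prevails.

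Other parts of the reply also stand:

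- Section 3.2.3 makes the table binding only where an interruption for toxicity is already required.
- If discontinuing may be temporary, a later restart after grade 3 is not flatly contradictory. The remaining fault is that the table makes restart the default, where section 3.2.5 provides no restart.
- There are other safeguards. Active or uncontrolled severe infection excludes a patient at entry. Section 3.2.5.1 says systemic imidazole antifungals, fluconazole included, should be avoided in all patients. Section 3.3.3 says moderate CYP3A4 inhibitors should be avoided if possible. Serious events are reviewed weekly (section 4.7), and the principal investigator should recommend actions in response (section 4.6). These are partial: the weekly review sets no dosing rule, and section 3.3.3 also allows everolimus at half dose with a moderate inhibitor such as fluconazole where one is required.

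Two stronger readings are tempting. A reader might infer that the protocol tells sites to continue 10 mg through an invasive fungal infection. That needs the infection to be graded 2 and tolerable; grading follows CTCAE v4.0, whose text is not in the documents, and nothing in them shows that this diagnosis can be grade 2. A reader might also infer that the protocol requires permanent discontinuation. Its own use of the term in sections 3.2.4 and 3.2.5.3 does not support that.

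**Conclusion.** The point holds as a minor safety inconsistency: wrong as written, low severity. The firm part is the grade 3 non-hematological row, where a hold under 3 weeks leads to restart one level lower with no exception for a diagnosis that section 3.2.5 treats separately. The grade 2 part is conditional on such an infection ever receiving that grade. Both parts assume that the site regards the infection as suspected drug toxicity; an infection judged unrelated falls outside the table.

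The number of patients affected cannot be derived from the documents. The sample size, power and PFS comparison do not depend on this instruction.

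**What to change.** In the grade 2 and grade 3 non-hematological rows of Table 3-1, add: *except invasive systemic fungal infection: discontinue study drug, see section 3.2.5*. This follows the form of the exceptions already in those rows and settles which text applies.

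Do not add the word permanently, in the table or in section 3.2.5. That would be a new clinical rule. If the sponsor wishes to allow or forbid a restart, it should decide that and state it in section 3.2.5.

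The cost is one phrase in two table rows, made by amendment, with no change to sample size, visits or analysis.
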